6.2 Report of Prior Investigations

6.2.1 Biocompatibility Evaluation

Biocompatibility testing was performed on all components of the product to demonstrate that the materials used are acceptable for the intended use. Biological safety testing has been successfully completed for the relevant device components; the devices are compliant with EN ISO 10993-1:2009 standard and FDA guidelines.

6.2.2 Clinical Studies

Results of 24 original research articles describing outcomes following ENB to aid in the diagnosis of peripheral lung lesions and mediastinal lymph nodes are summarized below. Based on the data in the table, the diagnostic yield weighted mean is 73.6% overall, 69.0% for studies published between 2005 and 2010, and 78.5% for studies published between 2011 and 2014. The overall pneumothorax weighted mean rate is 3.0%.

Table 1. Prior Clinical Studies

Study Lead Author and Citation	Study Design	N Pts.	Diagnostic Yield (%) Aided by ENB	Pneumothorax (%)
Balbo PE (6)	Retrospective, non-consecutive, single-center, single-arm	40	70.7	0.0
Becker HD (7)	Prospective, consecutive, single-center, single-arm	29	69.0	3.4
Bertoletti L (8)	Prospective, single-center	53	77.4	4.0
Brownback KR (9)	Retrospective, consecutive, single-center, single-arm	55	74.5	0.0
Diken ÖE (10)	Prospective, randomized, single-center	94	72.8	0.0
Eberhardt R (11)	Prospective, multi-center, randomized controlled trial	39	59.0	5.0
Eberhardt R (12)	Prospective, single-center	53	67.0	2.3
Eberhardt R (13)	Prospective, non-consecutive, multi-center, single-arm	89	75.5	1.9
Gildea TR (14)	Prospective, single-center, pilot study	58	74.0	3.5
Jensen KW (15)	Retrospective, consecutive, multi-center, single-arm	92	65.0	3.3
Karnak D (16)	Prospective	21	85.7	4.8
Karnak D (17)	Prospective, consecutive, single-center, single-arm	76	89.5	3.9
Khan AY (18)	Prospective, single-center, single-arm	24	75.0	0.0
Lamprecht B (19)	Retrospective, consecutive, single-center, single-arm	13	76.9	0.0
Lamprecht B (20)	Prospective, consecutive, single-center, single-arm	112	83.9	1.8
Loo FL (3)	Retrospective, consecutive, single-center, single-arm	40	94.0	0.0
Mahajan AK (21)	Retrospective, single-center, single-arm	48	77.0	10.2
Makris D (22)	Prospective, consecutive, single-center, single-arm	40	62.5	7.5
Mohanasundaram U (23)	Retrospective, single-center, single-arm	41	89.0	13.0
Odronic SI (24)	Retrospective, consecutive, single-center, single-arm	91	85.7	5.3

Table 1. Prior Clinical Studies

Study Lead Author and Citation	Study Design	N Pts.	Diagnostic Yield (%) Aided by ENB	Pneumothorax (%)
Pearlstein DP (25)	Retrospective, consecutive, single-center, single-arm	101	85.0	5.8
Schwarz Y (26)	Prospective, controlled, single-center	13	69.2	0.0
Seijo LM (27)	Prospective, consecutive, single-center, single-arm	51	67	0.0
Wilson DS (28)	Retrospective, consecutive, single-center, single-arm	248	69.8	1.2

Diagnostic yield defined as the proportion of subjects in whom ENB-directed biopsy yielded a diagnosis, as reported in the original article

7.0 Identification and Description of Device

7.1 Device Description

The superDimension™ navigation system is an image-guided localization system used to navigate endoscopic tools to targets in the lungs, such as lymph nodes and solitary pulmonary nodules. The superDimension™ navigation system consists of several reusable (non-sterile) hardware components used for ENB. A picture of the main console and a list of system components are shown below in Figure 1.

Localization system

- System cart
- Isolation transformer
- Location subsystem
- Uninterruptable power supply
- Industrial personal computer
- Touch screen monitor
- Location board
- Patient sensor triplet
- Sensor patches
- Keyboard
- Mouse
- Remote control
- Foot pedal

Currently available guiding catheter and accessory tools

- Locatable guide
- Extended working channel
- Edge locatable guide
- Edge extended working channel
- Edge extended working channel firm tip
- Bronchoscope adaptor
- Bronchoscope clip
- Patient sensors
- Localization components

Figure 1. superDimension™ Navigation System and Components

7.2 Indication and Contraindications

The System User Manual and the applicable *Instructions for Use* (IFU) will be the primary source of information for the system and components and will be kept current at each site throughout the study.

For detailed information regarding the indicated use of the device and contraindications, please refer to the System User Manual and applicable IFU(s).

7.3 Identification

The superDimension™ navigation system available at the clinical site will be used to conduct all ENB procedures. The system must have software version 6.0 or higher.

8.0 Study Design

Up to 2,500 consecutive subjects who undergo an ENB procedure using the superDimension™ navigation system will be enrolled at up to 75 global clinical sites. Consecutive subjects who

meet the eligibility criteria, sign informed consent, and undergo an ENB procedure using the superDimension™ navigation system will be included in the study. Subjects will be evaluated at baseline, procedure, 1 month, 12 months, and 24 months.

8.1 Study Objective

The objective of this prospective, single-arm, multicenter, post-market, observational, study is to evaluate outcomes following ENB procedures using the superDimension™ navigation system.

8.2 Endpoints

This post-market study is intended to capture clinical outcomes related to the real world use of ENB including but not limited to peripheral lesion biopsies, lymph node biopsies, fiducial market placement for radiation therapy, and tumor marking for diagnostic and therapeutic surgery.

The primary endpoint was chosen as a comprehensive safety endpoint that would be applicable to all ENB procedures being conducted as part of this study. The secondary endpoints are a combination of both safety and effectiveness endpoints that will be categorized in relation to intent of the ENB procedure being conducted.

8.2.1 Primary Endpoint

The primary endpoint is the incidence of pneumothorax related to the ENB index procedure rated as Grade 2 or higher according to the CTCAE scale.

8.2.2 Secondary Endpoints

The following secondary endpoints will be evaluated for all ENB index procedures:

1. Incidence of all pneumothorax related to ENB index procedure
2. Incidence of bronchopulmonary hemorrhage related to ENB index procedure rated as Grade 2 or higher according to CTCAE scale
3. Incidence of respiratory failure related to ENB index procedure rated as Grade 4 or higher according to CTCAE scale
4. Subject health status evaluated by EQ-5D questionnaire at all visits
5. Subject satisfaction evaluation at 1-month visit
6. ENB procedure effect on subject productivity and activity using the ENB Productivity and Activity Questionnaire (ENB-PAQ) at 1-month visit

The following secondary endpoints will be evaluated for all ENB index procedures performed for suspicion of cancer or other lung diseases in a lung lesion:

7. Diagnostic yield
8. Sensitivity
9. Specificity

CONFIDENTIAL

10. Positive predictive value (PPV)
11. Negative predictive value (NPV)
12. Repeat biopsy rate due to lack of diagnosis during ENB index procedure
13. Adequacy of sample for molecular testing and mutation type (if applicable)
14. Diagnosis
15. Stage at diagnosis (if applicable)

The following secondary endpoint will be evaluated for all ENB index procedures conducted for placement of fiducial markers:

16. Success rate of accurate placement of fiducial markers demonstrated through follow-up imaging.

The following secondary endpoint will be evaluated for all ENB index procedures conducted for dye marking in preparation for surgical resection.

17. Success rate of dye marking demonstrated by successful surgical resection

The following secondary endpoint will be evaluated for all ENB index procedures conducted for a lymph node biopsy:

18. Success rate of obtaining lymph node biopsy to provide stage of diagnosis.

8.3 Selection of Investigational Centers and Training Requirements

For this study, the following center selection criteria will be utilized.

- The center must have superDimension™ navigation system with Version 6 software or higher
- The center must have sufficient patient population, defined as the ability to perform at least five (5) ENB procedures per month
- There are no other ongoing studies that would prevent center from achieving enrollment goals
- The center has adequate research staff to conduct the study
- The center must be willing and able to comply with the Clinical Investigational Plan and data reporting requirements
- The center must be willing to enroll consecutive eligible subjects
- The center must have experience and/or ability to utilize the electronic data capture system
- The investigator(s) must be medically licensed
- The investigator(s) must have completed or be willing to complete the superDimension™ navigation system training course conducted by Medtronic

CONFIDENTIAL

Physicians in training (surgical residents, fellows) and Physician Assistants may assist the study investigator in the procedure as per standard procedures and practices at his/her institution; however, a study investigator must be the primary operator during the ENB procedure.

Each investigator participating in the clinical trial and the associated clinical study staff will receive training on the clinical protocol, as well as the ENB procedure utilizing the superDimension™ navigation system.

Medtronic will maintain a list of sites and investigators who are participating in the study; this information will be available on www.clinicaltrials.gov.

8.4 Subject Selection and Enrollment

After being informed of the nature of the study, the subject will sign a written informed consent form (ICF) that has been approved by the appropriate Institutional Review Board (IRB) or Ethics Committee (EC) of the respective clinical site. Following signing the informed consent form, the point of enrollment is defined as the time at which the ENB procedure is started. The start of the ENB procedure is defined as time of initial introduction of the Locatable Guide into the body.

Up to 2,500 subjects will be enrolled in the study at up to 75 sites. Subjects' participation in the study will last approximately 24 months

The ENB procedure will be performed per the System User Manual, applicable product IFU and the institution's standard practice. Subjects will be considered for the study if they meet specified inclusion criteria and none of the exclusion criteria. The criteria for enrollment must be followed explicitly.

8.4.1 Inclusion Criteria

1. Subject presents with lung lesion(s) requiring evaluation
2. Subject is willing and able to provide informed consent to participate in the study
3. Subject is candidate for elective ENB procedure
4. Subject is over the age of 18

8.4.2 Exclusion Criteria

1. The subject is unable or unwilling to comply with study follow-up schedule
2. The subject has participated in an investigational drug or device research study within 30 days of enrollment that would interfere with this study
3. Female subjects who are pregnant or nursing as determined by standard site practices

8.5 Withdrawal of Subjects

The reason for study exit of all enrolled subjects will be documented on the applicable electronic case report form (eCRF). In the event the subject withdraws consent during the study, the date of withdrawal will be documented. If the study investigator voluntarily removes a subject from

further study participation, supporting documentation must be in place for the rationale and date of removal. Every attempt will be made to contact subjects who are noncompliant. Subjects will be considered lost to follow-up once the following steps have been taken:

- Two phone calls should be made to the subject. Each attempt should be clearly documented in the source documents and the response or lack thereof should be captured.
- If there is no response to the phone calls, then certified letter should be written to the subject. A copy of the letter should be retained in the subject's source document.
- After a period of two (2) weeks following completion of the above actions, the subject will be considered Lost to Follow-up. The sponsor should be notified and the Study Exit form should be completed.

8.6 Study Procedures

8.6.1 Screening and Informed Consent

A baseline visit will be performed within 30 days prior to the scheduled procedure to assess study eligibility. Subjects will be approached to obtain written informed consent prior to any institution non-standard-of-care assessments or study specific data being collected. The purpose of the study and the benefits and risks of participating in the study will be explained to the subject and the consent process must be documented accordingly in the medical record. Subjects who agree to study participation must sign an IRB/EC approved ICF. Subjects will be informed that their participation in this study is voluntary and that they may refuse to participate or discontinue from the study at any time. Additionally, subjects will be informed that despite signing informed consent, the screening assessments may demonstrate the subject is not a suitable candidate for the study and may be withdrawn. Subjects will be given the opportunity to ask the investigator questions so that they are adequately informed about the research. A copy of the signed ICF must be provided to the subject.

If new information becomes available that may affect a subject's decision to continue to take part in the study, this information will be discussed with the subject.

8.6.2 Screen Failures

Subjects who provide study consent, but then are determined to be ineligible prior to the ENB procedure will be considered Screen Failures and will not require additional study follow-up visits. The reason for the Screen Failure will be clearly documented on the applicable eCRFs. Screen Failures will not be counted towards the number of study subjects.

8.6.3 ENB Procedures

The ENB procedure should be conducted in accordance with the System User Manual, applicable IFU and local institution standard of care.

CONFIDENTIAL

8.6.4 Study Schedule

Subjects will be evaluated at baseline, procedure, 1 month, 12 months, and 24 months post-index ENB procedure, as detailed below and in Table 2. All study data will be reported on the appropriate subject eCRFs.

8.6.4.1 Baseline

The following assessments will be performed within 30 days prior to the scheduled ENB procedure:

- Signed informed consent
- Eligibility criteria
- Demographics
- Medical history (including smoking history, lung history, anticoagulant and anti-platelet therapy medications, and risk factors)
- Quality of life questionnaire assessment utilizing EQ-5D

8.6.4.2 Procedure

The following procedures and assessments will be performed on the day of the index procedure (Day 0):

- Procedural information
- Lesion characteristics (if applicable)
- Biopsy results (if applicable)
- Adverse event assessment
- Lung cancer assessment
- Healthcare utilization

8.6.4.3 1 Month

It is preferred that the 1-month visit be conducted as in-person visit; however it will be acceptable to obtain the required information through a telephone visit with the subject. Additionally, a systematic review of the subject's medical records should be evaluated to ensure that all information is accurately reported.

The following procedures and assessments will be performed 1 month (± 7 days) post-index procedure:

- Adverse event assessment
- Lung cancer assessment
- Healthcare utilization
- Repeat biopsy results (if applicable)
- Quality of life assessment utilizing EQ-5D
- Patient satisfaction assessment

CONFIDENTIAL

- Productivity and activity assessment using the ENB-PAQ

8.6.4.4 12 and 24 Months

It is preferred that the 12 and 24 month visits be conducted as an in-person visit. However, it will be acceptable to obtain the required information through a telephone visit with the subject. Additionally, a systemic review of the subject’s medical records should be evaluated to ensure that all information is accurately reported.

The following procedures and assessments will be performed 12 months (± 30 days) and 24 months (± 30 days) post-index procedure:

- Adverse event assessment
- Lung cancer assessment
- Healthcare utilization
- Repeat biopsy results (if applicable)
- Quality of life assessment utilizing EQ-5D

8.6.5 Study Assessments Table

Table 2: Table of Assessments

	Baseline (Day -30 to 0)	Procedure (Day 0)	1 month (± 7 days)	12 months (± 30 days)	24 months (± 30 days)
Informed consent	X				
Eligibility criteria	X				
Demographics	X				
Medical history	X				
Procedural information		X			
Lesion characteristics (if applicable)		X			
Adverse event assessment		X	X	X	X
Lung cancer assessment		X	X	X	X
Healthcare utilization		X	X	X	X
Biopsy results (if applicable)		X	X	X	X
EQ-5D questionnaire	X		X	X	X
Patient satisfaction assessment			X		
ENB-PAQ			X		

9.0 Statistical Analysis

A separate statistical analysis plan (SAP) will be maintained to describe statistical methods and data analysis procedures.

9.1 General

All statistical analyses will be performed using Statistical Analysis System (SAS) for Windows (version 9.2 or higher, SAS Institute Inc. Cary, NC) or other widely accepted statistical or graphical software. In general, data for all study subjects combined will be presented. Individual data will be presented in subject listings.

Descriptive statistics will be used to present the data and to summarize the results. Discrete variables will be presented using frequency distributions and cross tabulations. Continuous variables will be summarized by presenting the number of observations (N), mean, standard deviation, median, minimum, and maximum values.

In general, data analysis will be conducted on all subjects who are enrolled in the trial and undergo an ENB procedure utilizing the superDimension™ navigation system. Analyses will be conducted on multiple subsets of study subjects based upon variables such as geography, demographics, investigator experience, lesion and procedure characteristics, and other variables as deemed appropriate. Results from interim and final analyses will be presented and/or published as defined in the Publication Plan.

9.2 Roll-in Subjects

For participating investigators who meet investigator selection criteria but do not have extensive experience conducting ENB procedures utilizing the superDimension™ navigation system, the investigator may be allowed to perform “roll-in cases”. A maximum of five (5) roll-in cases will be allowed per investigator. The purpose of the roll-in cases is to provide consistency in the physician user base within the study.

Final determination of eligibility for roll-in cases will be assessed as part of the investigator qualification process and will be documented in the study files.

Roll-in subjects will be considered study participants and will complete all protocol-required procedures and exams. However, data for the roll-in population will be analyzed separately from the remaining study population in an effort to detect any differences of outcomes related to level of investigator experience.

9.3 Sample Size Determination

No formal sample size estimates were conducted. The study is designed to include up to 2,500 subjects.

Each site will be allowed to enroll a maximum of 75 subjects into the study.

9.4 Analysis of Baseline Demographics and Procedural Characteristics

Descriptive statistics will be generated for pre-intervention demographics, procedural characteristics, and follow-up data collected. Categorical variables will be analyzed using frequency, incidence, and event rate. For continuous variables collected in the study, analysis will include mean, median, standard deviation, and range.

9.5 Endpoint Analysis

For the primary and secondary endpoints, descriptive statistics will be provided. The endpoints will be summarized using frequency measures such as count and percentage. For the primary endpoint, a 2-sided 95% exact binomial confidence interval will also be provided.

Adverse events for all enrolled subjects will be collected and reported for each follow-up visit. For adverse event reporting, which includes the primary and secondary endpoints, the primary analysis will be based on subject counts (e.g., the number and percentage of subjects with event among the total number of Subjects). The data will be presented in the format of p% (x/N) [e], with p and x being the percentage and number of subjects with events, respectively, N being the sample size of the analysis population, and e being the total number of events occurred in the x subjects. For example, the data of 2% (20/1000) [38] indicates that a total of 38 events occurred in 20 subjects out of a total of 1000 subjects (2%).

9.6 Handling of Missing Data

For the primary endpoint, the assessment is done peri-procedurally and it is projected that there will be minimal reduction in the eligible population based on the time of the measurement. Therefore, no imputations are planned for the primary endpoints.

9.7 Analysis Populations

Clinical data will be assessed in the following subject groups. Additional groups, such as country specific populations, may be assessed as deemed appropriate.

1. *Roll-in cohort*: defined as subjects identified as “roll-in subject” upon study enrollment (see Section 9.2).
2. *Primary cohort*: defined as all subjects who are enrolled in the trial and undergo and ENB index procedure utilizing the superDimension™ navigation system minus roll-in subjects
3. *Overall cohort*: defined as all subjects who are enrolled in the trial and undergo and ENB procedure utilizing the superDimension™ navigation system

9.8 Interim Analysis

Interim analyses will be conducted as defined in the publication plan. All interim analyses will be based on complete data for the specified follow-up timepoint. All interim analyses must be pre-specified and approved by the steering committee.

At a minimum, the following interim analyses will be conducted:

1. First 500 primary cohort subjects undergo ENB index procedure and complete the 1-month follow-up visit
2. First 1,000 primary cohort subjects undergo ENB index procedure and complete the 1-month follow-up visit
3. First 1,500 primary cohort subjects undergo ENB index procedure complete the 1-month follow-up visit

Additional interim analyses may be performed as appropriate.

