11.0 Adverse Events & Complications

Adverse events will be collected after the ENB index procedure has been initiated (defined as introduction of the Locatable Guide into the subject). During the course of the study, the following AEs will be collected and reported on the eCRF:

- All AEs related to the superDimension™ navigation system, associated tools, or ENB procedure (both index and any subsequent repeat ENB procedure)
- All deaths
- All pneumothoraxes
- All bronchopulmonary hemorrhages
- All respiratory failures

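### Do the interim analyses in Section 9.8 leave treated subjects who die or exit before the 1-month visit out of the safety rates?

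*Combined protocol and SAP*

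**What the plan says.** Section 9.8 requires at least three interim analyses. The first is given as "First 500 primary cohort subjects undergo ENB index procedure and complete the 1-month follow-up visit"; the items at 1,000 and 1,500 follow the same pattern (the third drops a conjunction, a clerical slip). The section adds "All interim analyses will be based on complete data for the specified follow-up timepoint", a sentence the synopsis repeats. It refers to the publication plan for the definition of interims, and asks that each be specified beforehand and cleared by the steering committee.

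Other sections bear on who is counted:

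- Section 9.7 defines the primary cohort as "all subjects who are enrolled in the trial and undergo and ENB index procedure utilizing the superDimension™ navigation system minus roll-in subjects". It sets no visit condition. It also says "Additional groups, such as country specific populations, may be assessed as deemed appropriate".
- Section 9.1 states "In general, data analysis will be conducted on all subjects who are enrolled in the trial and undergo an ENB procedure", and later "Results from interim and final analyses will be presented and/or published as defined in the Publication Plan".
- Section 9.5 states "Adverse events for all enrolled subjects will be collected and reported for each follow-up visit". Event rates are percentages of subjects, with N the size of the analysis population.
- Section 11.0 states "Adverse events will be collected after the ENB index procedure has been initiated". Its list covers every death, pneumothorax, bronchopulmonary hemorrhage and respiratory failure.

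Section 9.0 refers to a separate SAP for statistical methods. Neither that SAP nor the publication plan is in the text available for review.

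**The concern.** Section 9.8 names no interim denominator and no rule for a treated subject without a 1-month visit. The reference to complete data could be taken to mean that only subjects with the visit are analysed. On that reading, subjects who die, withdraw or are lost before the visit leave both numerator and denominator.

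Grade 5 (death) is part of the pneumothorax, hemorrhage and respiratory failure scales in Section 5.2. A subject who dies before the visit cannot complete it, so early fatal events would be zero by construction. Rates of non-fatal events could move either way, depending on who misses the visit. Because interim results are meant for presentation or publication, a safety rate conditioned on surviving and attending could reach readers as if it described everyone treated.

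**Working it through.** **Stated figure.** None to reproduce. The plan gives no sample-size calculation and no expected interim rate.

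**Inputs from the protocol.** Interim sizes 500, 1,000 and 1,500 (Section 9.8). Two-sided 95% exact binomial interval (Section 9.5). A proxy event rate from Section 10.1: chest tube drainage in 17/1,033 = 1.65%, printed as 1.6%. That rate is per nodule and is not the trial's endpoint.

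**Assumed inputs.** The documents give no 1-month death or dropout rate. I take 8, 16 and 24 events of Grade 2 or higher (1.60% at each size), one of them fatal before the visit. For non-fatal events I take a share q of 1% to 5% without the visit, and a risk ratio RR of 0.5 to 10 for subjects without the visit against those with it.

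**Step 1, the text.** Each item in Section 9.8 is a full clause: subjects undergo the procedure and complete the visit. It describes a state being reached, and no relative clause restricts who is counted. The subjects are those of the primary cohort, a term Section 9.7 defines by treatment alone. The sentence on complete data describes data; its ordinary sense is that no interim runs on a partly collected visit. Sections 9.1, 9.5 and 11.0 all run from treatment or enrolment, not from attendance.

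**Step 2, one early fatal event dropped, with the next completer filling the place.**

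| Set | All treated | Completers only |
|---|---|---|
| 500 | 8/500 = 1.60% (0.69% to 3.13%) | 7/500 = 1.40% (0.56% to 2.86%) |
| 1,000 | 16/1,000 = 1.60% (0.92% to 2.59%) | 15/1,000 = 1.50% (0.84% to 2.46%) |
| 1,500 | 24/1,500 = 1.60% (1.03% to 2.37%) | 23/1,500 = 1.53% (0.97% to 2.29%) |

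If the place is not filled, the first row becomes 7/499 = 1.40% (0.57% to 2.87%). The fatal-event rate itself goes from 1/500 = 0.20% (0.01% to 1.11%) to 0/500 (0% to 0.74%).

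**Step 3, non-fatal events.** Completer rate = p / (1 − q + q × RR), with p = 1.6%.

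- q = 1%: RR 0.5 gives 1.6/0.995 = 1.61%; RR 10 gives 1.6/1.09 = 1.47%.
- q = 5%: RR 0.5 gives 1.6/0.975 = 1.64%; RR 10 gives 1.6/1.45 = 1.10%.

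All of these lie inside the 8/500 interval of 0.69% to 3.13%.

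**Step 4, the milestone taken literally.** If every one of the first 500 treated subjects had to complete the visit, and each independently failed to do so with probability 0.5% or 1% (assumed), the condition would be met with probability 0.995^500 = 8% or 0.99^500 = 0.7%. Some handling of subjects without the visit is therefore needed in practice on either reading.

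**The case for a change.** The best case for a change is that the gap is real and cheap to close. Complete data is never defined, Section 9.7 leaves room for further analysis groups, and Step 4 shows that even the milestone reading needs a rule for missed visits. The numerical shift in the main rate is small, but turning one observed death into none is a different kind of error in a published safety report. Telephone visits and the record review in Section 8.6.4.3 may recover non-fatal events, but they cannot make a deceased subject a completer.

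What stands is that Section 9.8 does not spell out how a treated subject without the visit is counted, and a clarifying sentence would do no harm. What does not stand is that early deaths are left without any handling. They must be collected under Section 11.0, and Sections 9.5 and 9.7 place them in the numerator and denominator of the primary cohort. No rule in the plan directs an analyst to remove them. Section 9.8 already has a place for the remaining detail: the publication plan, with prior specification and steering committee approval.

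The documents also fix no waiting period for the data cut. The 10 working days in Table 3 run from learning of an event, and the two weeks in Section 8.5 run from completion of the calls and letter. Neither clock starts when the visit window closes.

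**Conclusion.** No change to the plan follows. Section 9.8 is short on detail, and the rest of the protocol fills the gap sensibly: the 1-month visit marks when the data are cut, and interim safety rates cover the treated primary cohort subjects in the set, early deaths included.

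The harm arises only on the less natural completer reading. There, one excluded fatal case would lower the rate by 0.20 percentage points at 500 (1.60% to 1.40%), 0.10 at 1,000 and 0.07 at 1,500. Differential loss of non-fatal events would give 1.10% to 1.64% against 1.60%. Every event count, loss rate and risk ratio behind these figures is assumed. The review summarised in Section 10.1 mentions no fatal event, and Section 9.6 expects little loss for a primary endpoint assessed around the procedure. The effect is confined to descriptive interim estimates. No interim test or stopping rule is stated, so no error rate is at stake, and the final cohorts are defined without a visit condition.

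The conclusion assumes that the separate SAP and the publication plan do not restrict the interim sets to subjects who completed the visit. If either does, the point should be reopened.
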